8.4.4.3 Patient Reported Outcomes

The LCSS completion rates, defined as the proportion of questionnaires actually received out of the expected number will be calculated and summarized at each assessment point. The EQ-5D (with two essential components: the EQ-5D descriptive system and the EQ visual analogue scale - EQ VAS) will be used to assess the subject's overall health status. The baseline and change from baseline of the EQ-5D and LCSS scores at each assessment point will be summarized using descriptive statistics. The disease-related symptom improvement rate at week 12 as measured by LCSS and its corresponding 95% CI will also be calculated by Clopper-Pearson method. All summaries for LCSS and EQ-5D will be done for all treated subjects, and also by tumor histology (SQ or NSQ), by subject subgroups, and all randomized subjects for Cohorts A and B.

8.5 Interim Analyses

There will be no formal interim analyses.

Data cuts for publication purposes will be performed until all subjects have completed the study, which is defined as the time point when the last subject enrolled had the opportunity for five year OS follow-up.

The final analysis will be performed when all subjects have completed the study,

9 STUDY MANAGEMENT

9.1 Compliance

9.1.1 *Compliance with the Protocol and Protocol Revisions*

The study shall be conducted as described in this approved protocol. All revisions to the protocol must be discussed with, and be prepared by, BMS. The investigator should not implement any deviation or change to the protocol without prior review and documented approval/favorable opinion from the IRB/IEC of an amendment, except where necessary to eliminate an immediate hazard(s) to study subjects.

If a deviation or change to a protocol is implemented to eliminate an immediate hazard(s) prior to obtaining IRB/IEC approval/favorable opinion, as soon as possible the deviation or change will be submitted to:

- IRB/IEC for review and approval/favorable opinion
- BMS
- Regulatory Authority(ies), if required by local regulations

Documentation of approval signed by the chairperson or designee of the IRB(s)/IEC(s) must be sent to BMS.

If an amendment substantially alters the study design or increases the potential risk to the subject: (1) the consent form must be revised and submitted to the IRB(s)/IEC(s) for review and approval/favorable opinion; (2) the revised form must be used to obtain consent from subjects currently enrolled in the study if they are affected by the amendment; and (3) the new form must be used to obtain consent from new subjects prior to enrollment.

If the revision is done via an administrative letter, investigators must inform their IRB(s)/IEC(s).

9.1.2 *Monitoring*

Representatives of BMS must be allowed to visit all study site locations periodically to assess the data quality and study integrity. On site they will review study records and directly compare them with source documents, discuss the conduct of the study with the investigator, and verify that the facilities remain acceptable.

In addition, the study may be evaluated by BMS internal auditors and government inspectors who must be allowed access to CRFs, source documents, other study files, and study facilities. BMS audit reports will be kept confidential.

The investigator must notify BMS promptly of any inspections scheduled by regulatory authorities, and promptly forward copies of inspection reports to BMS.

9.1.3 *Investigational Site Training*

Bristol-Myers Squibb will provide quality investigational staff training prior to study initiation. Training topics will include but are not limited to: GCP, AE reporting, study details and procedure, electronic CRFs, study documentation, informed consent, and enrollment of WOCBP.

9.2 *Records*

9.2.1 *Records Retention*

The investigator must retain all study records and source documents for the maximum period required by applicable regulations and guidelines, or institution procedures, or for the period specified by BMS, whichever is longer. The investigator must contact BMS prior to destroying any records associated with the study.

BMS will notify the investigator when the study records are no longer needed.

If the investigator withdraws from the study (eg, relocation, retirement), the records shall be transferred to a mutually agreed upon designee (eg, another investigator, IRB). Notice of such transfer will be given in writing to BMS.

9.2.2 *Study Drug Records*

It is the responsibility of the investigator to ensure that a current disposition record of investigational product (those supplied by BMS) is maintained at each study site where study drugs are inventoried and dispensed. Records or logs must comply with applicable regulations and guidelines and should include:

- amount received and placed in storage area
- amount currently in storage area
- label identification number or batch number
- amount dispensed to and returned by each subject, including unique subject identifiers
- amount transferred to another area/site for dispensing or storage
- nonstudy disposition (eg, lost, wasted)
- amount destroyed at study site, if applicable
- amount returned to BMS
- retain samples for bioavailability/bioequivalence, if applicable
- dates and initials of person responsible for Investigational Product dispensing/accountability, as per the Delegation of Authority Form.

BMS will provide forms to facilitate inventory control if the investigational site does not have an established system that meets these requirements.

9.2.3 Case Report Forms

An investigator is required to prepare and maintain adequate and accurate case histories designed to record all observations and other data pertinent to the investigation on each individual treated or entered as a control in the investigation. Data that are derived from source documents and reported on the CRF must be consistent with the source documents or the discrepancies must be explained. Additional clinical information may be collected and analyzed in an effort to enhance understanding of product safety. CRFs may be requested for AEs and/or laboratory abnormalities that are reported or identified during the course of the study.

For sites using the BMS electronic data capture tool, electronic CRFs will be prepared for all data collection fields except for fields specific to SAEs and pregnancy, which will be reported on the paper or electronic SAE form and Pregnancy Surveillance form, respectively. Spaces may be left blank only in those circumstances permitted by study-specific CRF completion guidelines provided by BMS.

The confidentiality of records that could identify subjects must be protected, respecting the privacy and confidentiality rules in accordance with the applicable regulatory requirement(s).

The investigator will maintain a signature sheet to document signatures and initials of all persons authorized to make entries and/or corrections on CRFs.

The completed CRF, including any paper or electronic SAE/pregnancy CRFs, must be promptly reviewed, signed, and dated by the investigator or qualified physician who is a subinvestigator and who is delegated this task on the Delegation of Authority Form. For electronic CRFs, review and approval/signature is completed electronically through the BMS electronic data capture tool. The investigator must retain a copy of the CRFs including records of the changes and corrections.

Each individual electronically signing electronic CRFs must meet BMS training requirements and must only access the BMS electronic data capture tool using the unique user account provided by BMS. User accounts are not to be shared or reassigned to other individuals.

9.3 Clinical Study Report and Publications

The Principal Investigator will be the signatory for the clinical study report.

The data collected during this study are confidential and proprietary to BMS. Any publications or abstracts arising from this study require approval by BMS prior to publication or presentation and must adhere to BMS's publication requirements as set forth in the approved clinical trial agreement (CTA). All draft publications, including abstracts or detailed summaries of any proposed presentations, must be submitted to BMS at the earliest practicable time for review, but at any event not less than 30 days before submission or presentation unless otherwise set forth in the CTA. BMS shall have the right to delete any confidential or proprietary information contained in any proposed presentation or abstract and may delay publication for up to 60 days for purposes of filing a patent application.

10 GLOSSARY OF TERMS

Term	Definition
Adverse Reaction	An adverse event that is considered by either the investigator or BMS as related to the investigational product
Unexpected Adverse Reaction	An adverse reaction, the nature or severity of which is not consistent with the applicable product information (eg, Investigator Brochure for an unapproved investigational product)
Serious Adverse Event	Serious adverse event defined as any untoward medical occurrence that at any dose: results in death; is life threatening (defined as an event in which the subject was at risk of death at the time of the event; it does not refer to an event which hypothetically might have caused death if it were more severe), requires inpatient hospitalization or causes prolongation of existing hospitalization; results in persistent or significant disability/incapacity, is a congenital anomaly/birth defect; is an important medical event (defined as a medical event(s) that may not be immediately life threatening or result in death or hospitalization but, based upon appropriate medical and scientific judgment, may jeopardize the subject or may require intervention [eg, medical, surgical] to prevent one of the other serious outcomes listed in the definition above). Examples of such events include, but are not limited to, intensive treatment in an emergency room or at home for allergic bronchospasm; blood dyscrasias or convulsions that do not result in hospitalization.). For reporting purposes only, BMS also considers the occurrence of pregnancy, overdose (regardless of association with an AE), and cancer as important medical events.

11 LIST OF ABBREVIATIONS

Term	Definition
AE	adverse event
ALT	alanine aminotransferase
AST	aspartate aminotransferase
AT	aminotransaminases
HCG	Human chorionic gonadotrophin
BMS	Bristol-Myers Squibb
BP	blood pressure
BUN	blood urea nitrogen
C	Celsius
CBC	complete blood count
CI	confidence interval
CNS	Central nervous system
CR	Complete response
CRF	Case Report Form, paper or electronic
CYP	cytochrome p-450
dl	deciliter
ECG	electrocardiogram
ECOG	Eastern Cooperative Oncology Group
eCRF	Electronic Case Report Form
EDC	Electronic Data Capture
EEG	electroencephalogram
eg	exempli gratia (for example)
FDA	Food and Drug Administration
FSH	follicle stimulating hormone
GCP	Good Clinical Practice
h	hour
HBsAg	hepatitis B surface antigen
HBV	hepatitis B virus
HCV	hepatitis C virus
HIV	Human Immunodeficiency Virus

Term	Definition
HR	heart rate
HRT	hormone replacement therapy
ICH	International Conference on Harmonisation
ie	id est (that is)
IEC	Independent Ethics Committee
IMP	investigational medicinal products
IND	Investigational New Drug Exemption
IRB	Institutional Review Board
IHC	immunohistochemistry
IU	International Unit
IV	intravenous
kg	kilogram
LCSS	Lung Cancer Symptom Scale
LDH	lactate dehydrogenase
mg	milligram
min	minute
mL	milliliter
mmHg	millimeters of mercury
MTD	maximum tolerated dose
μg	microgram
N	number of subjects or observations
N/A	not applicable
NIMP	non-investigational medicinal products
NSAID	nonsteroidal anti-inflammatory drug
NSCLC	Non-small cell lung cancer
NSQ	Nonsquamous
ORR	Objective response rate
OS	Overall survival
PD	Progressive disease
PD-1	Programmed death-1

Term	Definition
PD-L1	Programmed death- ligand 1
PK	pharmacokinetics
PR	Partial response
PRO	Patient reported outcomes
PS	Performance status
RBC	red blood cell
SAE	serious adverse event
SD	standard deviation
SQ	Squamous
T-HALF	Half life
WBC	white blood cell
WHO	World Health Organization
WOCBP	women of childbearing potential

APPENDIX 1 RECIST 1.1 CRITERIA

This Appendix has been excerpted from the full RECIST 1.1 criteria. For information pertaining to RECIST 1.1 criteria not contained in the study protocol or in this Appendix, please refer to the full publication.¹

1 ASSESSMENT OF OVERALL TUMOR BURDEN AND MEASURABLE DISEASE

To assess objective response or future progression, it is necessary to estimate the overall tumor burden at baseline and use this as a comparator for subsequent measurements. Measurable disease is defined by the presence of at least one measurable lesion.

1.1 Measurability of tumor

At baseline, tumor lesions/lymph nodes will be categorized measurable or non-measurable as follows. All baseline evaluations should be performed as close as possible to the treatment start and never more than 4 weeks before the beginning of the treatment.

Measurable lesions must be accurately measured in at least one dimension (longest diameter in the plane of the measurement to be recorded) with a minimum size of:

- 10 mm by CT scan - (CT scan slice thickness no greater than 5 mm)
- 10 mm caliper measurement by clinical exam (lesions which cannot be accurately measured with calipers should be recorded as non-measurable)
- 20 mm by chest x-ray
- Malignant lymph nodes: To be considered pathologically enlarged and measurable, a lymph node must be ≥ 15 mm in short axis when assessed by CT scan (CT scan slice thickness recommended to be no greater than 5 mm). At baseline and in follow-up, only the short axis will be measured and followed.

All measurements should be recorded in metric notation, using calipers if clinically assessed.

Special considerations regarding lesion measurability

Bone lesions:

- Bone scan, PET scan or plain films are not considered adequate imaging techniques to measure bone lesions. However, these techniques can be used to confirm the presence or disappearance of bone lesions.
- Lytic bone lesions or mixed lytic-blastic lesions, with identifiable soft tissue components, that can be evaluated by cross sectional imaging techniques such as CT or MRI can be considered as measurable lesions if the soft tissue component meets the definition of measurability described above.
- Blastic bone lesions are non-measurable.

Cystic lesions:

- Lesions that meet the criteria for radiographically defined simple cysts should not be considered as malignant lesions (neither measurable nor non-measurable) since they are, by definition, simple cysts.
- Cystic lesions' thought to represent cystic metastases can be considered as measurable lesions, if they meet the definition of measurability described above. However, if non-cystic lesions are present in the same patient, these are preferred for selection as target lesions.

Lesions with prior local treatment:

- Tumor lesions situated in a previously irradiated area, or in an area subjected to other loco-regional therapy, are usually not considered measurable unless there has been demonstrated progression in the lesion.

Non-measurable lesions are all other lesions, including small lesions (longest diameter < 10 mm or pathological lymph nodes with 10 to < 15 mm short axis), as well as non-measurable lesions. Lesions considered non-measurable include: leptomeningeal disease, ascites, pleural or pericardial effusion, inflammatory breast disease, lymphangitic involvement of skin or lung, abdominal masses/abdominal organomegaly identified by physical exam that is not measurable by reproducible imaging techniques.

1.2 Method of assessment

The **same method of assessment and the same technique should be used** to characterize each identified and reported lesion at baseline and during follow-up. Imaging based evaluation should always be performed rather than clinical examination unless the lesion(s) being followed cannot be imaged but are assessable by clinical examination.

CT, MRI: CT is the best currently available and reproducible method to measure lesions selected for response assessment. Measurability of lesions on CT scan is based on the assumption that CT slice thickness is 5 mm or less. When CT scans have slice thickness greater than 5 mm, the minimum size for a measurable lesion should be twice the slice thickness.

Chest x-ray: Chest CT is preferred over chest x-ray, particularly when progression is an important endpoint, since CT is more sensitive than x-ray, particularly in identifying new lesions. However, lesions on chest x-ray may be considered measurable if they are clearly defined and surrounded by aerated lung.

Clinical lesions: Clinical lesions will only be considered measurable when they are superficial and ≥10 mm diameter as assessed using calipers. For the case of skin lesions, documentation by color photography including a ruler to estimate the size of the lesion is suggested. As noted above, when lesions can be evaluated by both clinical exam and imaging, imaging evaluation should be undertaken since it is more objective and may be reviewed at the end of the study.

Ultrasound: Ultrasound is not useful in assessment of lesion size and should not be used as a method of measurement. If new lesions are identified by ultrasound in the course of the study, confirmation by CT or MRI is advised.

Endoscopy, laparoscopy: The utilization of these techniques for objective tumor evaluation is not advised.

Tumor markers: Tumor markers alone cannot be used to assess objective tumor response.

2 BASELINE DOCUMENTATION OF ‘TARGET’ AND ‘NON-TARGET’ LESIONS

Target lesions: When more than one measurable lesion is present at baseline all lesions up to a maximum of five lesions total (and a maximum of two lesions per organ) representative of all involved organs should be identified as target lesions and will be recorded and measured at baseline.

Target lesions should be selected on the basis of their size (lesions with the longest diameter), be representative of all involved organs, and should lend themselves to reproducible repeated measurements.

Lymph nodes merit special mention since they are normal anatomical structures which may be visible by imaging even if not involved by tumor. Pathological nodes which are defined as measurable and may be identified as target lesions must meet the criterion of a short axis of ≥ 15 mm by CT scan. Only the short axis of these nodes will contribute to the baseline sum. All other pathological nodes (those with short axis ≥ 10 mm but < 15 mm) should not be considered non-target lesions. Nodes that have a short axis < 10 mm are considered non-pathological and should not be recorded or followed.

A sum of the diameters (longest for non-nodal lesions, short axis for nodal lesions) for all target lesions will be calculated and reported as the baseline sum diameters. The baseline sum diameters will be used as reference to further characterize any objective tumor regression in the measurable dimension of the disease.

Non-target lesions: All other lesions (or sites of disease) including pathological lymph nodes should be identified as non-target lesions and should also be recorded at baseline. Measurements are not required and these lesions should be followed as ‘present’, ‘absent’, or ‘unequivocal progression’. In addition, it is possible to record multiple non-target lesions involving the same organ as a single item on the case record form (eg, ‘multiple enlarged pelvic lymph nodes’ or ‘multiple liver metastases’).

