3 TUMOR RESPONSE EVALUATION AND RESPONSE CRITERIA

3.1 Evaluation of target lesions

Complete Response (CR): Disappearance of all target lesions. Any pathological lymph nodes (whether target or non-target) must have reduction in short axis to < 10 mm.

Partial Response (PR): At least a 30% decrease in the sum of diameters of target lesions, taking as reference the baseline sum diameters.

Progressive Disease (PD): At least a 20% increase in the sum of diameters of target lesions, taking as reference the smallest sum on study (this includes the baseline sum if that is the smallest on study). In addition to the relative increase of 20%, the sum must also demonstrate an absolute increase of at least 5 mm. Note: the appearance of one or more new lesions is also considered progression.

Stable Disease (SD): Neither sufficient shrinkage from the baseline study to qualify for PR nor sufficient increase to qualify for PD, taking as reference the smallest sum diameters while on study.

Special notes on the assessment of target lesions

- **Lymph nodes:** Lymph nodes identified as target lesions should always have the actual short axis measurement recorded and should be measured in the same anatomical plane as the baseline examination, even if the nodes regress to below 10 mm on study. This means that when lymph nodes are included as target lesions, the 'sum' of lesions may not be zero even if complete response criteria are met, since a normal lymph node is defined as having a short axis of < 10 mm.
- **Target lesions that become 'too small to measure' :** All lesions (nodal and non-nodal) recorded at baseline should have their actual measurements recorded at each subsequent evaluation, even when very small (eg, 2 mm). If the radiologist is able to provide an actual measure, that should be recorded, even if it is below 5 mm.

However, when such a lesion becomes difficult to assign an exact measure to then:

- i. if it is the opinion of the radiologist that the lesion has likely disappeared, the measurement should be recorded as 0 mm.
- ii. if the lesion is believed to be present and is faintly seen but too small to measure, a default value of 5 mm should be assigned (note: in case of a lymph node believed to be present and faintly seen but too small to measure, a default value of 5 mm should be assigned in this circumstance as well). This default value is derived from the 5 mm CT slice thickness (but should not be changed with varying CT slice thickness).

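### Appendix 1 excludes pathological nodes of 10 to <15 mm from the non-target lesions, contradicting the rest of the appendix and leaving these nodes without a category

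*Combined protocol and SAP*

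**What the plan says.** Appendix 1, Section 2 sorts lymph nodes by short axis. To be a target lesion, a node "must meet the criterion of a short axis of ≥ 15 mm by CT scan". Of the middle band, the other pathological nodes with a short axis of at least 10 but under 15 mm, the text says that they "should not be considered non-target lesions". For the smallest nodes: "Nodes that have a short axis < 10 mm are considered non-pathological and should not be recorded or followed".

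The non-target paragraph of the same section, which follows after the paragraph on the sum of diameters, says: "All other lesions (or sites of disease) including pathological lymph nodes should be identified as non-target lesions and should also be recorded at baseline".

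Two other parts of the appendix bear on the middle band. Section 1.1 includes "pathological lymph nodes with 10 to < 15 mm short axis" among the non-measurable lesions. Section 3.1 makes this a condition of complete response: "Any pathological lymph nodes (whether target or non-target) must have reduction in short axis to < 10 mm". Section 3.2 adds that, for non-target CR, every node must be below 10 mm.

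Investigators apply these criteria (protocol Section 5.4.1), and Section 5.9 marks central assessments as not applicable. ORR, PFS and DOR are exploratory endpoints (Section 8.3.3).

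**The concern.** The two statements in Section 2 cannot both be followed. The first calls these nodes pathological and removes them from the only class open to them; the second puts pathological nodes into that class. This is an operational scoring rule, not background text. Sites could resolve the conflict differently, and the protocol describes no central read that would bring them into line.

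What is at stake is how a persisting or growing node of this size is scored. That can alter best overall response, the date of progression, and two decisions tied to progression: treatment beyond progression (Section 4.3.4) and Cohort B retreatment (Sections 3.1 and 4.1).

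**Working it through.** No figure in the plan depends on this sentence, so there is nothing to recompute. The check is a comparison of the rules, followed by a trace of one node through them.

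**Category by node size**

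| Short axis | Can be target? | Non-target under the disputed sentence? | Non-target under the rest of the appendix? |
|---|---|---|---|
| 15 mm or more | Yes | Yes, if not chosen as target | Yes, if not chosen as target |
| 10 to <15 mm | No | No | Yes |
| Under 10 mm | No | No (not pathological) | No (not pathological) |

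Only the middle row differs. Under the disputed sentence it holds nodes that are pathological but have no category. A middle band distinct from the under-10 mm band serves a purpose only if its nodes are non-target. The CR wording in Section 3.1 likewise presumes that a pathological node is one or the other. The disputed sentence is therefore the outlier.

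**Does anything else settle it?** The opening of Appendix 1 sends the reader to the full RECIST publication only for matters that neither the protocol nor the appendix contains. This matter is contained, so that fallback does not apply.

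**Trace of a node measuring 12 mm at baseline (illustrative size)**

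1. *All target lesions disappear and the node stays at 12 mm.* Recorded as non-target, it scores Non-CR/non-PD, and Appendix Table 1 gives PR. Uncategorised, the subject can be scored CR unless the assessor applies the node conditions in Sections 3.1 and 3.2. Under Section 8.3.3 both CR and PR count towards ORR, so ORR does not change; the CR/PR split does.
2. *Target lesions are stable and the node enlarges substantially.* Recorded as non-target, it can be judged for unequivocal progression, giving overall PD. Uncategorised, the non-target progression rule in Section 3.2, which covers existing non-target lesions, has nothing to act on, and the status can stay SD.
3. *The same node is instead called a new lesion.* Any new lesion gives PD in Appendix Table 1, whereas Section 3.2 says a modest increase in a non-target lesion is usually not enough. The error can therefore run either way: progression missed, or called on a lower threshold.
4. *Treatment continues beyond progression.* Section 4.3.4 measures further progression from the time of initial PD and counts new measurable lesions, including nodes once they reach 15 mm. An old node labelled as new could enter that sum.

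Items 2 to 4 can move PFS, DOR and the progression date. Item 1 can move best overall response.

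**The case against.** The strongest reply is that the rest of the appendix limits the harm. Much of that stands.

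- A reader might infer that sites will leave these nodes unrecorded. The text does not say so. It withdraws a label; the instruction not to record or follow applies only to nodes under 10 mm. Section 5.4.1 also requires known or suspected disease sites to be assessed at screening and afterwards.
- A reader might infer that false CRs will follow. Sections 3.1 and 3.2 both require nodes to fall below 10 mm, so the risk is confined to assessors who overlook those conditions.
- A false new-lesion call is restrained by Section 3.3, which requires a new lesion to be unequivocal. A node visible on the baseline scan should not qualify.
- Missed progression needs a substantial increase confined to such nodes, with no target progression and no genuine new lesion.
- The wording may have come late. Revised Protocol 04, dated 01-Dec-2017, lists an update to the RECIST appendix. The synopsis gives 6.5 years in total with 5 years of follow-up for the last subject, implying 6.5 − 5 = 1.5 years of accrual. Even counted from Amendment 04 in December 2014, accrual would end around mid-2016. If the sentence entered with Revised Protocol 04, few or no baselines were recorded under it. The documents give neither actual enrolment dates nor the earlier appendix text, so this stays open.

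These points reduce the likely effect. They do not remove the contradiction, and none tells a site which sentence to follow.

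**Conclusion.** The contradiction is real and the sentence is wrong as it stands: it conflicts with the non-target paragraph of its own section and with Sections 1.1, 3.1 and 3.2 of the appendix. The consequence is a possible, not a demonstrated, misclassification. It may reach investigator-assessed exploratory PFS, DOR and best overall response, and the progression date behind treatment beyond progression and Cohort B retreatment.

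The primary and secondary objectives concern select adverse events and are unaffected, as is the sample size.

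No count of affected subjects can be given. The documents do not state how many subjects had nodes of this size, how sites read the rule, or when the wording entered. A figure for the planned 1280 subjects would rest wholly on assumed shares. For retreatment, only subjects randomised to Cohort B could be affected.

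The conclusion that the word *not* is the error rests on the appendix alone, since every other relevant statement in it points the same way.

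**What to change.** Delete the word *not* from the sentence in Appendix 1, Section 2, so that pathological nodes of 10 to <15 mm are non-target lesions, as in the rest of the appendix. Send sites a one-line clarification.

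Then make two checks: in which protocol version the wording first appeared, and how the CRF captured nodes of this size at baseline. Query baseline records only if the checks show that such nodes were omitted. If they were, review the response and progression records of those subjects before the exploratory efficacy analyses.

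The cost is one word, a short notice to sites and a look at document history and CRF design. Any data query is conditional on the result.
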